2.2. Secondary Objectives

[figure not shown]
- Describe Ophthalmology visit patterns before and during treatment, investigating the specific adverse event of interest (keratopathy) as available.
- Explore the magnitude and sources of distress for these patients via the National Comprehensive Cancer Network Distress Thermometer (NCCN DT) instrument, as already collected in the DCI clinics per routine care.
- Describe the health care resource utilization (HCRU) at Duke Health for patients receiving BLENREP.

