3.4.1. Patient Characteristics

The following patient characteristics will be measured as listed in the table below. Demographics will be summarized for the most recent measures on or prior to the index date, and all the other characteristics (i.e., clinical characteristics) will be abstracted at each clinic visit thereafter, until the end of follow-up. The end of follow-up will be defined as the date of the last clinical encounter available in the database prior to the IRB cut-off date.

Category	Variable	At Baseline	At Subsequent Clinical Encounters
Demographics	Age: Defined as of the index year.	x	
	Age groups: Patients will be assigned to one of the following age groups: 18-34, 35-44, 45-54, 55-64, 65-74, 75+.	x	
	Sex: Male, Female, Unknown	x	
	Weight	x	
	Height	x	
	Body mass index	x	

	Current Payer type: Whether the patient is covered by commercial, Medicaid, Medicare, self-insured, or was missing insurance payer type.	x	
	Race	x	
	RRMM diagnosed by DCI (yes/no)	x	
Comorbid Conditions	NCI Comorbidity Index	x	
Clinical Characteristics of RRMM	
 Subtype (e.g., IgA, IgG, light chain only, etc.) Cytogenetics Immunologic Studies Molecular testing results 	x	
Administered systemic treatments for MM prior to index	
 Medication Name Start/end dates of treatment Reason for discontinuation or change of treatment Line of therapy Prior HCST 	x	x
Treatment with BLENREP	
 Start/Re-start and end dates of treatment (as applicable) Dosing Line of therapy Reasons for discontinuation or delays of therapy 	x	x
NCCN Distress Thermometer	
 DT Score Problem List items 	x	x
Clinical Outcomes assessments	
 Myeloma markers (differs per patient and MM subtype; includes M-spike, UPEP, serum free light chains, etc.) Physician Reported Notes Disease response if available (using IMWG response criteria) Lab tests/assessments Death, if documented 		x
Ophthalmologic Status	
 Date of eye exam and results, as available. Documentation of ocular-toxicity 		x
HCRU	
 Disease-related hospitalizations Disease-related ED visits Disease-related outpatient visits 		x

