3.6. Data Analysis Considerations

Analyses will be undertaken by Duke University statisticians with expertise in patient-centered outcomes research. Details of the analyses will be furthered described in the statistical analysis plan (SAP) to be created at a later date.

Primary Objectives: Describe patient characteristics and treatment patterns for patients treated with BLENREP

Patient demographics and clinical characteristics (including diagnosis, laboratory measurements, general symptoms, and other comorbidities) will be summarized using descriptive statistics, consisting of the mean (\pm standard deviation [SD]) and median (with interquartile range [IQR]) values for continuous variables and frequency distributions and proportions for categorical variables.

Demographics will be described for the most recent measures on or prior to the index date. Clinical outcomes will be described until the end of follow-up. The end of follow-up will be defined as the date of the last clinical encounter available in the database prior to the IRB cut-off date. Summary statistics such as mean (\pm SD) and median (with IQR) values for continuous variables and frequency distributions and proportions for categorical variables will be calculated.

Time to clinical outcomes (i.e., time to response, duration of response, OS) will be analyzed using Kaplan-Meier analysis and median times to event will be reported (if the medians are achieved). 95% CIs will be reported in addition to the medians.

Treatment use and treatment patterns will be summarized using proportions (i.e., proportion of patients with select treatment for the control of symptoms). Sequences of treatment will also be described.

Secondary Objective: Describe Ophthalmology visit patterns and events

To the extent that they are available, events related to Ophthalmology outcomes (i.e., eye exams, outpatient visits, treatments for ocular toxicity, and other related HCRU events) will be summarized by the mean (\pm SD) and median (with IQR) number of events per patient per year and by the proportion and frequency distribution of patients with any occurrence of the respective

outcome. Treatment use and treatment patterns associated with ocular toxicity will be summarized using proportions (i.e., proportion of patients with select treatment for the control of symptoms).

Secondary Objective: Explore magnitude and sources of distress for these patients

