The main outcome variable is the occurrence of actionable distress, defined as a NCCN DT score of 4 or higher. This outcome is clinically relevant because it is aligned with the medical practice guidelines for management of distress in cancer patients. The analysis will describe the proportion of clinic visits where actionable distress is reported during treatment with BLENREP, and the frequency of actionable distress over time.

Sources of distress will be assessed using the NCCN DT Problem List by examining the proportion of visits where types of problems are reported (e.g., physical or emotional problems). The frequency of individual types of problems, and the most commonly-reported problems will be examined descriptively.

Secondary Objective: Describe healthcare resource utilization (HCRU)

To the extent that they are available, HCRU (i.e., inpatient admissions, treatment-related outpatient visits, and emergency department visits) will be summarized by the mean (\pm SD) and median (with IQR) number of events per patient per year and by the proportion and frequency distribution of patients with any occurrence of the respective outcome. Likewise, mean (\pm SD) and median (with IQR) length of stay per year will be summarized for inpatient visits.

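### Eye-event and HCRU rates have no stated window or denominator, and the only follow-up defined runs past BLENREP, although the eye objective covers only the time before and on treatment

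*Combined protocol and SAP*

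**What the plan says.** - **Objectives (2.2).** The eye objective is "Describe Ophthalmology visit patterns before and during treatment, investigating the specific adverse event of interest (keratopathy) as available". The HCRU objective is "Describe the health care resource utilization (HCRU) at Duke Health for patients receiving BLENREP", with no time limit.
- **Collection (3.4.1).** Items other than demographics "will be abstracted at each clinic visit thereafter, until the end of follow-up". The end point is set as follows: "The end of follow-up will be defined as the date of the last clinical encounter available in the database prior to the IRB cut-off date". The variables table marks Ophthalmologic Status and HCRU for subsequent encounters only, with no baseline mark for either. BLENREP start, re-start and end dates are collected.
- **Analysis (3.6).** For the eye objective, "events related to Ophthalmology outcomes (i.e., eye exams, outpatient visits, treatments for ocular toxicity, and other related HCRU events") are summarised by mean and median yearly number per patient and by the proportion of patients with any occurrence. HCRU is handled the same way, with length of stay also given per year. No start, stop or person-time denominator is stated for either. The sentence "Clinical outcomes will be described until the end of follow-up" stands under the Primary Objectives.
- **Contrast (3.6, distress).** The proportion of visits with actionable distress is described "during treatment with BLENREP, and the frequency of actionable distress over time".

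**The concern.** A yearly rate needs a defined period, used for both the events and the person-time. Here the plan defines one follow-up period only, and it ends at the last encounter, not at the end of BLENREP or the start of a later therapy. An analyst who takes that default will count time that the eye objective does not cover. The eye-visit rate would then no longer describe monitoring on BLENREP. It would also depend on how long each patient was seen after stopping.

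The part of the objective before treatment has the opposite problem: no eye data are marked for collection before index. For HCRU, a single figure over all follow-up would combine care on BLENREP with care during later therapy or at the end of life, and the reader could not tell them apart.

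**Working it through.** **1. The windows side by side**

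| Item | Objective (2.2) | Collection (3.4.1) | Analysis (3.6) |
|---|---|---|---|
| Eye events | before and on treatment | subsequent encounters, to last encounter | yearly rate and any event; no window |
| HCRU | no window | subsequent encounters, to last encounter | yearly rate and any event; no window |
| Distress | no window | baseline and subsequent encounters | on BLENREP for the actionable-distress proportion; no limit stated for the Problem List |

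For eye events the three columns do not match. The objective includes a period with no marked collection (before index), and collection includes a period outside the objective (after BLENREP).

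**2. Room for post-treatment time.** Starts run from 5 August 2020 to 22 November 2022, which is 839 days, and the minimum follow-up is one month (3.3.1). The IRB cut-off date is not given. Time after BLENREP can therefore differ widely between patients, but its length cannot be derived.

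**3. Effect on the eye-visit rate.** The plan gives no rate, treatment duration or follow-up length, so there is no figure to reproduce and every input below is an assumption. With time in months and rates per year,

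R = [r_on × T_on + r_off × (T_tot − T_on)] / T_tot.

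Take r_on = 12 and r_off = 0 or 4:

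| T_on | T_tot | R, r_off = 0 | R, r_off = 4 | Share of on-drug rate |
|---|---|---|---|---|
| 8 | 12 | 96/12 = 8.0 | (96 + 16)/12 = 9.33 | 67% to 78% |
| 4 | 12 | 48/12 = 4.0 | (48 + 32)/12 = 6.67 | 33% to 56% |
| 4 | 24 | 48/24 = 2.0 | (48 + 80)/24 = 5.33 | 17% to 44% |
| 2 | 24 | 24/24 = 1.0 | (24 + 88)/24 = 4.67 | 8% to 39% |

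If r_off = r_on, or if T_tot = T_on, then R = 12 (100%) and there is no dilution.

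**4. Any-occurrence proportion.** A patient with an event on treatment also has one in any longer window that contains the treatment period. Adding time can only leave this proportion unchanged or raise it.

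**5. HCRU.** Use the same formula with an assumed on-drug rate of 1 event a year and 0.5 to 3 a year afterwards. For T_on = 2 and T_tot = 24, R runs from (2 + 0.5 × 22)/24 = 0.54 to (2 + 3 × 22)/24 = 2.83, so it can fall or rise. The share of counted events that fall after BLENREP runs from (0.5 × 4)/(8 + 0.5 × 4) = 20% (T_on = 8, T_tot = 12, r_off = 0.5) to 66/68 = 97% (T_on = 2, T_tot = 24, r_off = 3).

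**6. Stability of short windows.** Two visits in one month on drug annualise to 2 × 12 = 24 a year. With up to about 30 patients (3.5), a few such values can dominate a mean of per-patient rates.

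**The case against.** The strongest reply is that this is silence, not error. Section 3.4.1 fixes how long data are collected, and collecting to last contact does not fix the window of a rate. The sentence that carries outcomes to the end of follow-up belongs to the primary objectives. Sections 3.4 and 3.6 defer details to a later SAP. This stands in part: a reader might infer that the plan commits to all follow-up for eye events and HCRU, and the documents do not say so. What remains is that the only period on offer does not fit the eye objective, and that the missing baseline mark affects abstraction, which a later analysis document cannot repair.

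Four further readings are tempting and go too far.

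- *That HCRU over all follow-up contradicts its objective.* The objective names the patients and sets no time limit, so it can be read as the whole cohort over all follow-up. The word treatment-related in 3.6 qualifies outpatient visits only and does not name the treatment.
- *That the eye objective is on-treatment only.* It also covers the time before treatment, and a remedy that starts at first dose would omit that part.
- *That distress as a whole is restricted to time on BLENREP.* The limit is attached to the proportion of visits with actionable distress. The Problem List analysis states none.
- *That a particular dilution, such as a rate cut to one third, has been shown.* It depends wholly on assumed rates and durations, and some assumptions give none.

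An on-treatment window also has a cost: less person-time and unstable per-patient rates. That is a reason to choose the summary carefully, not to leave the window open.

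**Conclusion.** The point holds as a mismatch between the eye objective, the collection schedule and an analysis with no window. If the default follow-up is used, post-BLENREP time enters the eye-visit rate. Dilution then requires visits to be less frequent off drug, which is plausible but not documented. Its size cannot be computed from the documents; the assumed inputs above give anything from 8% of the on-drug rate to no dilution at all. The absence of a baseline mark for Ophthalmologic Status needs no assumption: the pre-treatment part of the objective has no marked data. For HCRU the weaker conclusion applies. The all-follow-up figure is admissible but unlabelled as to period, and its direction of change is unknown. The changes should be made before abstraction is complete.

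**What to change.** In 3.6:

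- Report eye-event rates for a pre-index period of stated length and for an on-treatment period. The latter runs from first BLENREP dose to last dose plus a lag fixed in the SAP, ending earlier at the next myeloma therapy, death or end of follow-up. State how gaps and re-starts are counted.
- Use the same window for events and person-time, and show post-BLENREP time separately.
- Report HCRU for the same on-treatment and post-treatment periods, alongside the all-follow-up figure.
- Give each rate as total events over total person-time as well as per patient.

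In 3.4.1:

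- Mark Ophthalmologic Status for baseline collection.
- Make the start date of the next myeloma therapy an explicit field. The systemic-treatment row is labelled as prior to index yet also marked for subsequent encounters, and 3.6 plans to describe treatment sequences, so the date may already be intended but is not clearly listed.

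The cost is SAP wording, one or two extra items from the same chart, additional table columns, and less person-time and lower precision in each period. The BLENREP dates needed to split the time are already collected.

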2. OBJECTIVES

This study aims to describe the real-world use of BLENREP and associated patterns of care, including dosing and dose modification, and eye care specialist visits, and associated healthcare utilization and clinical outcomes in patients with relapsed and/or refractory multiple myeloma (RRMM) seen in the Duke Cancer Institute (DCI) clinics.

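### The healthcare-use events to be collected do not match those to be analysed, and the pre-treatment part of the eye-visit objective has no planned data

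*Combined protocol and SAP*

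**What the plan says.** **Healthcare resource utilization (HCRU).** The secondary objective in 2.2 is "Describe the health care resource utilization (HCRU) at Duke Health for patients receiving BLENREP". It names no cause of use. Section 2 puts the aim more loosely, as "eye care specialist visits, and associated healthcare utilization and clinical outcomes". The HCRU row of the 3.4.1 table lists "Disease-related hospitalizations Disease-related ED visits Disease-related outpatient visits", marked for subsequent encounters only. Section 3.6 then analyses "inpatient admissions, treatment-related outpatient visits, and emergency department visits", and adds that "length of stay per year will be summarized for inpatient visits". Neither disease-related nor treatment-related is defined.

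**Eye visits.** The objective in 2.2 is "Describe Ophthalmology visit patterns before and during treatment", qualified by availability. The Ophthalmologic Status row in 3.4.1 holds "Date of eye exam and results, as available. Documentation of ocular-toxicity". Its baseline column is blank and only the subsequent-encounter column is marked. Section 3.6 summarises eye events per patient per year and as the proportion of patients with any event, without dividing the time before treatment from the time on it.

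**Context.** Section 3.4 calls the variables general descriptions and leaves operational detail to a SAP, which 3.6 says is still to be written. Section 3.1 states that data are abstracted by hand into a REDCap form, and 3.7 that the form is piloted and revised. Section 4 discloses undercounting of care outside the network, but no restriction of HCRU by cause.

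**The concern.** In a descriptive study, the definition of a count largely determines what the result means. Here the objective, the collected variables and the analysis describe three different sets of events. Section 1 presents corneal toxicity as the drug's distinctive problem, and section 2 asks about utilization that goes with its use. An abstractor who applies disease-related literally could leave out an admission or visit caused by the drug and not by the myeloma. The resulting table could still be headed inpatient admissions and ED visits, with nothing in the limitations to warn the reader.

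For the eye objective the stake is simpler. A comparison of visit patterns before and during treatment needs pre-treatment visits, and the form as described does not ask for them. Because abstraction is manual, a later SAP cannot analyse events that were never recorded.

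**Working it through.** There is no planned figure to reproduce: 3.5 states that no power or sample-size calculation is needed. The check sets the sections side by side.

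| Item | Objective (2.2) | Collected (3.4.1) | Analysed (3.6) |
|---|---|---|---|
| Inpatient admissions | no cause limit | disease-related | no qualifier |
| ED visits | no cause limit | disease-related | no qualifier |
| Outpatient visits | no cause limit | disease-related | treatment-related |
| Length of stay | not named | not listed | summarised |
| Eye visits before treatment | included | baseline not marked, no look-back | not separated |
| Eye visits during treatment | included | marked | not separated |

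**Step 1, HCRU.** In none of the three event types do all three columns agree. For outpatient visits, collection and analysis carry different qualifiers, so neither can be shorthand for the other. For admissions and ED visits, 3.6 merely lacks the adjective. It may be an abbreviated reference to the 3.4.1 variables, or it may mean all admissions and ED visits; the text does not settle which. On either reading the collected set is narrower than the wording of 2.2. Length of stay can be derived if admission and discharge dates are abstracted, but the table does not list those dates.

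**Step 2, eye visits.** The question is whether the blank baseline cell means anything. Other non-demographic rows in the same table are marked at baseline: comorbidity index, myeloma subtype, prior systemic treatments and the Distress Thermometer. The column is therefore used for clinical items where they are wanted, and the blank is informative. The eye row does record exam dates, and the BLENREP row records start, re-start and end dates, so once pre-index exams are abstracted the split needs no new variable.

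**Step 3, rates (secondary).** Section 3.6 gives events per patient per year without naming the person-time. Section 3.3.1 admits patients with encounters at least 1 month after index, so follow-up could be about 1/12 year. One event in that time enters as 1 ÷ (1/12) = 12 per year. With about 30 patients (3.5), that one event adds 12/30 = 0.40 per year to the mean. This is an illustration only: it assumes a patient at the minimum, and the follow-up distribution is not given.

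**The case against.** The strongest reply is that much of this is wording. Section 3.4 offers general descriptions and a SAP is to follow; 3.6 may simply be summarising the 3.4.1 variables without repeating the adjective; and the reference in section 2 to associated utilization does not require all-cause capture. That stands for admissions and ED visits, so a reader should not infer that those results will certainly be misreported. It does not explain the treatment-related label on outpatient visits, and it cannot recover events that the form never requests.

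A second reply is that disease-related is undefined, so abstractors might well include toxicity events. That also stands: the loss is possible, not established.

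A third is that both plans are qualified by availability. That qualifier covers gaps in the source record, not items that nobody is asked to abstract. The EHR may well hold pre-index eye exams.

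Three stronger readings are not supported:

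- A reader might take "events related to Ophthalmology outcomes (i.e., eye exams, outpatient visits, treatments for ocular toxicity, and other related HCRU events" to include eye-related admissions and ED visits. The closing phrase is open and does not say so.
- Collecting eye data past the end of treatment might look like a defect. It is not, because the recorded dates allow a cut at analysis.
- The 3.4.1 statement that clinical items are abstracted after index might look like a bar on all pre-index data. The table's own baseline marks for other clinical rows contradict that.

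On rates, the planned median and the proportion with any event already soften the effect of a short follow-up.

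**Conclusion.** The point holds as an inconsistency between what is to be described, collected and analysed. The conflict over outpatient visits and the absence of planned pre-treatment eye data are plain on the text. The narrower collection of admissions and ED visits is a risk that depends on how abstractors apply an undefined term. Its size cannot be estimated, since the documents give no event counts and no breakdown by cause. Only secondary descriptive results are affected; no hypothesis test or primary result depends on it. The change is worth making because the correction is cheap now and harder once charts have been abstracted. The person-time point is minor and would not justify a change by itself.

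**What to change.** While the case report form is being piloted:

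1. **One HCRU event set in 3.4.1 and 3.6.** Preferably abstract all Duke inpatient admissions, with admission and discharge dates, and all ED visits, each with a related/not-related flag, and use one definition of outpatient visits in both sections. At minimum, carry the disease-related label into 3.6, state in 2.2 and in section 4 that HCRU is restricted to it, and say whether treatment toxicity counts as related.
2. **Eye data.** Mark Ophthalmologic Status at baseline with a stated look-back start. In 3.6, summarise eye visits separately before and during treatment, using exam dates and the BLENREP start, re-start and end dates already collected.
3. **Optional, in the SAP.** Name index to end of follow-up as the HCRU person-time, and report total events over total person-time beside the planned mean and median.

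The cost is a small form change, a short abstraction rule for the flag, and some extra abstraction and judgement for about 30 patients. If abstraction has already begun, completed charts would have to be reopened. Eye visits outside the network will still be missed.

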3.3. Study Population

3.3.1. Inclusion Criteria

To be included in the final study sample, patients must meet the following inclusion criteria provided below:

- Age \geq 18 years of age as of start of treatment with Belantamab mafodotin - blmf
- Patients with a corresponding ICD-9 or ICD-10 diagnosis code consistent with multiple myeloma seen at Duke.
- Patients with a record of starting treatment with Belantamab mafodotin - blmf for RRMM between August 5, 2020 and November 22, 2022.
- Patients having healthcare encounters at DCI \geq 1-month post index

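### The any-occurrence proportions for eye and HCRU outcomes carry no time window or censoring rule, so for events that accrue over time they depend on how long patients were observed

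*Combined protocol and SAP*

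**What the plan says.** Section 3.6 gives eye and HCRU outcomes the same pair of summaries. For HCRU the plan reports the mean and median annual event count per patient, and also summarises each outcome "by the proportion and frequency distribution of patients with any occurrence of the respective outcome". The ophthalmology paragraph uses the same construction. No time window, horizon or treatment of censoring is attached to the proportion in either place.

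Three other provisions determine how long each patient is observed:

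- Section 3.3.1 sets the minimum. It admits "Patients having healthcare encounters at DCI" at least 1 month after index.
- Section 3.3.1 also sets the start window: treatment must begin "between August 5, 2020 and November 22, 2022".
- Sections 3.4.1 and 3.6 set the end of follow-up, "defined as the date of the last clinical encounter available in the database" before the IRB cut-off. That cut-off has no calendar date.

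Kaplan-Meier analysis is planned in section 3.6 for time to response, duration of response and overall survival, but not for eye or HCRU events. Section 2.2 frames the ophthalmology objective as covering the periods before and during treatment; section 3.6 does not say which period the eye proportion refers to. Section 4 does not list unequal follow-up among the limitations. Section 3.6 leaves further analysis detail to a SAP still to be written.

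**The concern.** A crude proportion treats a patient watched for 1 month without an admission exactly like one watched for 2 years without an admission. When observation is unequal by design, the result mixes the risk of the event with the length of observation. A patient censored alive before a given time is counted as event-free to that time, which understates the risk.

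At stake is a figure that readers are likely to quote: the share of patients admitted, seen in the ED or treated for ocular toxicity. As planned it has no time attached, so it cannot be read as a risk by any stated month, and setting it beside another series requires knowing both follow-up distributions. The annual rate in the same sentence does not supply this. It describes event burden, not how many patients are affected by a given time.

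**Working it through.** **No plan figure to reproduce.** The documents give no event rate, incidence or follow-up length for these outcomes. The only related count is the cohort in section 3.5: about 30 patients less about 2 clinical-trial participants, 30 − 2 = 28, before later starters, stated there as up to approximately 30.

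**Range of follow-up.** The minimum is about 1 month (section 3.3.1). The start window, 5 August 2020 to 22 November 2022, spans 839 days: 839 / 365.25 × 12 = 27.6 months. If the cut-off falls after that window closes, the earliest starters have potential follow-up above 2 years. This is a maximum; death or an early last encounter shortens it.

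**Events that accrue over time.** Assume a constant first-event hazard h per month and no deaths. The risk by month t is 1 − exp(−ht). If follow-up is uniform on a to b months, the expected crude proportion is

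1 − [exp(−ha) − exp(−hb)] / [h(b − a)].

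At an assumed 0.6 per year, h = 0.05 per month:

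- 1 to 9 months: 1 − (0.951 − 0.638) / 0.40 = 22%
- 1 to 18 months: 1 − (0.951 − 0.407) / 0.85 = 36%
- 1 to 27.6 months: 1 − (0.951 − 0.252) / 1.33 = 47%

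With 28 patients, the first and last are about 6 and 13 patients (28 × 0.216 = 6.0; 28 × 0.474 = 13.3) at the same hazard. The risk at fixed times does not depend on the follow-up mix: 14% at 3 months, 26% at 6 and 45% at 12.

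Range over assumed hazards:

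| Hazard per year | Crude, 1 to 9 months | Crude, 1 to 27.6 months | Risk at 12 months |
|---|---|---|---|
| 0.3 | 12% | 29% | 26% |
| 0.6 | 22% | 47% | 45% |
| 1.0 | 33% | 63% | 63% |

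In the longer scenario the crude figure happens to lie near the 12-month risk. In the shorter one it is about half of it or less. The crude figure alone does not tell a reader which situation applies.

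**Events that occur early.** Assume 70% of patients are ever affected, with median onset m of 0.5, 1 or 1.5 months among them, so h = ln 2 / m and the formula above is multiplied by 0.7. The crude proportion is 70%, 68% and 66% on 1 to 27.6 months, and 68%, 64% and 58% on 1 to 9 months. The largest gap between the two follow-up patterns is 8 percentage points, against 26 for the accruing event at 0.6 per year (47.4 − 21.6).

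**Does the annual rate cure it?** Section 3.6 does not say whether the rate averages individual annualised rates or pools person-time. If individual rates are averaged, one event in 1 month becomes 12 per year. Either way it remains a rate, not a proportion affected by a stated time.

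**The case against.** The strongest reply is that the plan already scales for observation time. Every eye and HCRU outcome has an annualised count in the same sentence, and the proportion is its companion. That stands. A reader might infer that these outcomes are reported only as a crude proportion, and the text does not support that.

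A reader might also infer that the proportion reflects length of observation as much as risk, or that it is biased low because patients died. Neither is supported. The size depends on event rates and timing that the documents do not give, and it is small for early events. A patient who dies without an admission is a fully observed non-event, and a competing-risk analysis counts that patient the same way. The downward bias comes only from patients censored alive.

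It is fair, too, that the illustrated percentages compare hypothetical follow-up patterns, whereas this study has one cohort and no control group. They show how sensitive the statistic is; they do not estimate an error in this study. A count of patients with any event is a legitimate description of what was observed, so it need not be removed. Finally, the outcomes are secondary, descriptive and reported as available, in about 30 patients, with detail deferred to a later SAP. That lowers the severity. It does not supply the missing window.

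**Conclusion.** The point holds in limited form. The any-occurrence proportion lacks a time window and a censoring rule, and for admissions, ED visits and later ocular treatments it moves with length of observation. Under the assumed hazards of 0.3 to 1.0 per year, it roughly doubles between short and long follow-up (12% to 29% and 33% to 63% at the two ends). These figures rest on a constant hazard, uniform follow-up and no deaths, none of which comes from the documents, and follow-up beyond 2 years is potential only.

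A reader might go further and conclude that every outpatient-visit proportion is near 100% by construction. That fits only treatment-related oncology visits, because section 1 describes outpatient administration and section 3.3.1 requires a later DCI encounter. Neither makes an ophthalmology visit near-certain, and that proportion serves the objective in section 2.2.

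This is a cheap improvement of modest severity.

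**What to change.** In section 3.6, or in the SAP to which it defers:

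- For inpatient admissions, ED visits and on-treatment ocular events and treatments, add the cumulative incidence of the first event at fixed times from first BLENREP dose, for example 3, 6 and 12 months. Use the Aalen-Johansen estimator with documented death as a competing event, censor at the end of the patient's observation window, and give 95% CIs and numbers at risk.
- State the observation window for each outcome. For eye outcomes, say whether it ends with treatment or with follow-up.
- Keep the crude n/N only if it is labelled with that window and with median follow-up.
- Summarise pre-treatment eye visits separately, since an analysis starting at first dose cannot cover that part of the objective.
- Keep the ophthalmology visit proportion. The treatment-related oncology outpatient proportion is uninformative and can be left out.

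The cost is wording and a few lines of code. Treatment dates, eye-exam dates and death, if documented, are already listed in section 3.4.1. The HCRU rows there do not mention dates explicitly, so the case report form should be checked for admission and ED dates. The downsides are wide intervals at 12 months with about 30 patients, and possible under-capture of deaths, which would leave some deaths treated as censoring.
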